4.3.2 Primary Safety Endpoint

The ST Monitoring Feature will be evaluated by the percentage of patients with false positive events. The percentage of patients with false positive events is calculated as the number of patients who experience false positives divided by the number of evaluable patients. A False Positive occurs when a clinical event does not occur within 72 hours following a Type I ST episode.

The hypothesis is formally expressed as follows:

H_0 : Percent of patients experiencing a false positive event in 12 months $\geq 15\%$

H_a : Percent of patients experiencing a false positive event in 12 months $< 15\%$

The desired outcome is to reject the null hypothesis at the 2.5% significance level. The null hypothesis will be rejected at the 2.5% significance level if the

Statistical Analysis Plan

upper bound of the 95% confidence interval for the percent of patients experiencing false positive events is less than 15%. The upper confidence bound will be calculated using the Wilson score interval method.

Patient Group

All enrolled patients who have a successful implant or system revision, complete the baseline follow up visit and have the ST Monitoring Feature and Patient Notifier turned ON will be included in the evaluation of this study endpoint. Data collection towards the study endpoint will begin after the Baseline visit.

Further, the analysis population for the primary safety endpoint will be those subjects with the Fortify[®] ST (upgraded), Fortify Assura[®] ST and Ellipse[®] ST. Data from subjects with a Fortify[®] ST device prior to being upgraded will not be included in this analysis.

Analysis

Primary Analysis

The primary analysis will be a complete case analysis where patients who are lost to follow-up before completing their 12 month visit without experiencing a false positive event will be considered non-evaluable and omitted from the analysis of the endpoint. Patients experiencing a false positive event and withdrawing before the 12 month visit will be included in the analysis. The proportion of patients experiencing false positives will be estimated by the number of patients experiencing a false positive event divided by the number of evaluable patients.

Imputation Analysis

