4.3.3 Secondary Safety Endpoint

The ST Monitoring Feature will be evaluated by the False Positive Rate (FPR). The False Positive Rate is calculated as the number of false positives per patient-year of follow-up. A False Positive occurs when there is a Type I ST episode that is not followed by a clinical event within 72 hours. Only ST segment shift events that occur beyond the baseline visit will be included in this analysis.

$$\text{FPR} = \frac{\text{\#of false positive events}}{\text{patient years of follow-up}}$$

The hypothesis is formally expressed as follows:

H₀: Expected FPR ≥ 1.9 per patient-year of follow-up

H_a: Expected FPR < 1.9 per patient-year of follow-up

The desired outcome is to demonstrate that the False Positive Rate is less than 1.9 events per patient-year. The null hypothesis will be rejected at the 2.5% significance level if the 97.5% upper confidence limit (UCL) for the expected FPR is less than 1.9 per patient-year of follow-up.

Statistical Analysis Plan

Patient Group

All enrolled patients who have a successful implant or system revision and have completed the Baseline visit with the ST Monitoring Feature and Patient Notifier programmed ON will be included in this endpoint.

Further, the analysis population for the secondary safety endpoint will be those subjects with the Fortify® ST (upgraded), Fortify Assura® ST and Ellipse® ST devices. The data from subjects with a Fortify® ST prior to being upgraded will not be included in this analysis.

Analysis

Primary Analysis

The expected FPR will be estimated by the observed FPR. To avoid imbalance in the number of false positives that each patient with false positives contributes, the maximum number of false positives from a patient that will be counted toward meeting the requirement on the number of false positives will be two. In addition, for a single follow up period (i.e. one interrogation and device evaluation to the next), if multiple false positive events occur, only one event will be counted toward the analysis. This will prevent multiple false positives that occur before the physician has the opportunity to evaluate the patient and reprogram the device from contributing to an imbalance in the data. For any patients with more than two false positives their follow up time will be truncated to the date of the second false positive.

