The analysis will be carried out where only those false positives counted toward meeting the requirement of number of false positives are included. That is, if a patient has experienced more than two false positives, only the first two false positives of that patient will be included.

The 97.5% upper confidence limit for the expected FPR will be calculated based on the confidence interval calculation of a Poisson rate using the exact method (Ulm, 1990)⁶. The null hypothesis will be rejected at the 2.5% significance level if the 97.5% upper confidence limit is less than 1.9 per patient-year.

Additional Analyses

Empirical analyses will be provided for the false positive rate using

1. the estimator described in the Primary Analysis section, and
2. the estimator that uses all false positive events.

The standard error of these empirical estimators will be calculated as the standard deviation of their bootstrap distributions. The bootstrap distributions will be

Statistical Analysis Plan

constructed using 1,000 bootstrap resamples. Each bootstrap resample will be performed at the patient level (in order to preserve the correlation structure between events with a given patient), and each resample will have a total sample size equal to the total number of evaluable patients. The bootstrap distributions will be used to estimate two-sided 95% bootstrap confidence intervals.

Subgroup Analysis

The analysis of the secondary safety endpoint will be performed on the following subgroups of patients

- Coronary artery disease patients with cardiomyopathy
- Coronary artery disease patients without cardiomyopathy
- Patients with abnormal baseline ECGs, for each of six abnormal subgroup categories
- Patients with normal baseline ECGs
- Patients with arrhythmias
- Gender
- Patients alerted via Merlin.net and patients alerted via device Patient Notifier

[figure not shown]
Sample Size

[REDACTED]

[REDACTED]

[REDACTED]

[REDACTED]

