4.5 Overall sample size and data cut-off

[figure not shown]
The total number of patients required for enrollment in order to satisfy the primary endpoints and the secondary endpoint is driven by the sample size requirement to satisfy the primary efficacy endpoint. Thus the total sample size required for this study is 5,228.

Data collection for the purposes of the FDA market approval application will be considered to be complete when the primary safety endpoint data are available and at least 41 clinical events have occurred.

Following submission of the clinical data, patients will continue to be followed until closure of the study for providing long-term follow up on the Investigational Devices.

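### The secondary false positive rate test caps every patient at two events but stops follow-up only for patients with more than two, which over 12 months in effect moves the goal from 1.9 to about 2.14 per patient-year

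*Protocol*

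**What the plan says.** Section 4.3.3 defines the endpoint without a cap: "The False Positive Rate is calculated as the number of false positives per patient-year of follow-up". The null hypothesis is an expected rate of 1.9 per patient-year or more, tested at 2.5%.

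The primary analysis of this endpoint then sets the counting rules:

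- No patient contributes more than two events; beyond that, "only the first two false positives of that patient will be included".
- Within one interval between device evaluations, "if multiple false positive events occur, only one event will be counted toward the analysis".
- Time at risk is shortened only in one group: "For any patients with more than two false positives their follow up time will be truncated to the date of the second false positive".

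The upper limit is "based on the confidence interval calculation of a Poisson rate using the exact method". An estimator using all false positives appears only under Additional Analyses, next to the capped one. For both, "The standard error of these empirical estimators will be calculated as the standard deviation of their bootstrap distributions", with resampling by patient. The SAP repeats all of this. The sample-size text for the endpoint is redacted in both documents.

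**The concern.** A rate is estimated without bias under a cap if observation ends when the cap is reached, whatever happens afterwards. Here it ends at the second event only if a third event later occurs. Patients who go on to a third event lose the time after their second. Patients who do not go on keep it. The rule therefore keeps event-free time and discards time that contains events, so the ratio falls below the true rate even under the Poisson model that the plan uses for its limit.

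At stake is what a formally tested safety statement means. A result reported as a false positive rate below 1.9 at the 2.5% level would not carry that error. A second question follows: the hypothesis is worded for all false positives while the statistic uses capped ones, and the visible text does not say on which scale 1.9 was set.

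**Working it through.** **Inputs.** From section 4.3.3: goal 1.9 per patient-year, one-sided 2.5%, cap of two, truncation only above two, exact Poisson limit (reject if chi-square(0.975; 2D+2)/(2 × patient-years) < 1.9, with D counted events). From section 3.1: 12 months of follow-up. Assumed: n = 100 and 500, and a common rate for all patients in steps 1 to 4. The one-per-interval rule is left out, except where step 4 names it.

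**1. Counted events per patient.** Let N be Poisson with mean 1.9 (rate λ = 1.9, T = 1 year). P(0) = 0.1496, P(1) = 0.2842, P(2) = 0.2700, P(N≥3) = 0.2963, P(N≥4) = 0.1253.
E[min(N,2)] = P(1) + 2·P(N≥2) = 0.2842 + 2 × 0.5663 = 1.4167.

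**2. Expected time as written.** Given N = k events, the second falls on average at 2T/(k+1). Summing over k ≥ 3 gives (2/λ)·P(N≥4), so
time = T·P(N≤2) + (2/λ)·P(N≥4) = 0.7037 + 1.0526 × 0.1253 = 0.8356 years.
Counted rate = 1.4167 / 0.8356 = **1.695**.

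**3. Expected time with truncation at two or more.**
time = T·P(N≤1) + (2/λ)·P(N≥3) = 0.4337 + 1.0526 × 0.2963 = 0.7456 years.
Counted rate = 1.4167 / 0.7456 = **1.900**.
The difference, 0.0900 years per patient, is 0.2700 × 1/3: the time kept by patients with exactly two events.

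**4. Effective goal and error.** The effective goal is the true rate at which the counted rate, as written, equals 1.9.

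| Follow-up | Counted rate at true 1.9 | Effective goal | Error at true 1.9, n = 100 / 500 |
|---|---|---|---|
| 0.5 y | 1.785 | 2.03 | about 5% / 23% |
| 1 y | 1.695 | 2.14 | about 23% / 89% |
| 2 y | 1.713 | 2.09 | about 29% / 89% |
| 3 y | 1.806 | 1.99 | about 12% / 35% |

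The error columns are simulated; repeated runs at 12 months gave 23% to 24% and 89% to 90%. With truncation at two or more the error is about 2.2%, so under equal rates the wording causes all of the inflation. At n = 500 and 12 months, rejection falls to about 40% at a true rate of 2.0, 5% at 2.1 and 0.2% at 2.2.

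The one-per-interval rule removes events but not time, so it lowers the counted rate further. With truncation at two or more and an assumed device evaluation 3 or 14 days after each alert, the counted rate is 1.88 or 1.82 instead of 1.900.

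**5. Rates that differ between patients (assumed gamma, 12 months, truncation at two or more).**

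- If 1.9 is meant for all false positives: with shape 2 and a mean of 1.9, the counted rate is 1.60 and false rejection is about 48% at n = 100. The cap removes most from the patients with most events.
- If 1.9 is meant for counted false positives: with mean rates set so that the counted rate is 1.9 (2.343, 2.901 and 4.502 for shapes 2, 1 and 0.5), the exact Poisson limit rejects in about 4% to 8% of trials. A log-scale limit from the patient-level bootstrap standard error rejects in 2.1% to 2.5% at n = 100 and 500.

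**6. Link to the primary safety endpoint.** It requires a Wilson upper bound "for the percent of patients experiencing false positive events is less than 15" per cent. At n = 500 the largest passing count is 59 patients (upper bound 14.92%; 60 gives 15.14%). If data stop at 12 months, the other 441 patients each give a full year, so the counted rate is at most 2 × 59 / 441 = 0.27, with an exact upper limit of 0.32.

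**The case against.** **The error figures are boundary figures.** At exactly 1.9, any downward bias drives the error towards 100% as n grows. A reader might infer from 89% that a device with a far higher rate would pass. Step 4 shows otherwise: the goal shifts by about 13% at 12 months (2.14 / 1.9), and rejection is rare from 2.2 upwards. This stands, and the shift is the better summary.

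**Such a device would fail anyway.** At a common rate of 1.9, 1 − exp(−1.9) = 85% of patients would have a false positive within a year, far above the primary 15% limit. This also stands: the fault cannot by itself carry a poor device through both tests. It still leaves the secondary test without its stated error.

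**The goal may already be on the capped scale.** The counting rules refer to a required number of false positives that is not visible, and the sample-size text is redacted. It is tempting to say that an uncapped goal is tested with a capped count. The documents do not establish that. The truncation fault is present on either reading.

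**Repeat false positives are not ignored.** The all-event estimator has a planned 95% bootstrap interval, and the DSMB reviews the rate. Correct, although neither decides the test.

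**Conclusion.** The truncation rule is wrong as written and biases the tested rate low. At a common true rate of 1.9 over 12 months the counted rate is 1.695, equivalent to a goal of about 2.14 (1.99 to 2.09 at the other follow-up lengths checked). The error at exactly 1.9 is about 23% at n = 100 and 89% at n = 500. These errors depend on illustrative sizes and equal rates; the direction of the bias does not depend on n.

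The need to name the scale of 1.9, and to replace the Poisson limit, rests on rates varying between patients. The plan itself expects this, since it caps events to avoid imbalance and resamples by patient, but the gamma distributions are assumptions.

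A reader might infer from step 6 that any trial passing the primary endpoint passes this test automatically, however many repeat alarms occur. That holds only if the false positive rate data are cut at 12 months. Section 4.5 makes data collection "complete when the primary safety endpoint data are available and at least 41 clinical events have occurred", so follow-up can run longer. First false positives after month 12 then break the bound: in the extreme case at n = 500 it becomes 2 × 500 / 441 = 2.27.

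This should be fixed, as a correction to a secondary endpoint.

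**What to change.** 1. In section 4.3.3 of both documents, change the truncation condition from more than two to two or more, so that time stops at the second counted false positive for every patient who reaches it.
2. State in the hypothesis whether 1.9 refers to counted or to all false positives.
   - *Counted:* restate the hypothesis and goal as the capped rate. The effect of the one-per-interval rule is then part of the definition.
   - *All:* report the planned all-event estimator and its bootstrap limit against 1.9 alongside the capped test, since correction 1 does not close that gap when rates vary.
3. Replace the exact Poisson limit by estimate × exp(1.96 × SE / estimate), with SE the planned patient-level bootstrap standard deviation, and reject if this is below 1.9.
4. State the data cut for this endpoint. If it is 12 months, say that passing the primary endpoint implies passing the capped test.

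The cost is one wording change, one sentence on scale and one interval formula, using estimators and resampling already planned. The limit becomes slightly less favourable and wider, and the redacted sample-size justification must be rechecked. The all-event estimate has its own weakness: a few patients with many alarms can move it, and its simulated error on this log scale was 1.2% to 4.1% at n = 100 and 2.2% to 2.9% at n = 500.

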4.4 Analysis of Efficacy

4.4.1 Primary Efficacy Endpoint

The efficacy endpoint will be evaluated as the sensitivity of the ST Monitoring Feature to detect clinical events. Sensitivity of the ST Monitoring Feature to detect clinical events will be calculated as the number of True Positive events (as defined in section 3.2.3) divided by the total number of ACS clinical events.

$$\text{Sensitivity} = \frac{\text{\# of TP events}}{\text{Total number of ACS events}}$$

A clinical event is considered to be related to the onset of a Type I ST episode if the clinical event occurs within 72 hours after the onset of a Type I ST episode.

The hypothesis is formally expressed as follows:

H_0 : Sensitivity \leq 50%

H_a : Sensitivity $>$ 50%

The desired outcome is to demonstrate that the sensitivity of the ST Monitoring Feature is greater than 50%. The null hypothesis will be rejected at the 2.5% significance level if the lower bound of the 95% confidence interval for sensitivity is greater than 50%. The lower confidence bound will be calculated using the Wilson score interval method.

Patient Group

All enrolled patients who have a successful implant or system revision, complete the Baseline follow up visit and have the ST Monitoring Feature and Patient Notifier turned ON, and experience clinical events will be included in the evaluation of this study endpoint. Data collection towards the study endpoint will begin after the Baseline visit.

Further, the analysis population for the primary efficacy endpoint will be those subjects with the Fortify[®] ST (upgraded), Fortify Assura[®] ST and Ellipse[®] ST devices. The data from subjects with a Fortify[®] ST prior to being upgraded will not be included in this analysis.

Statistical Analysis Plan

Analysis

Primary Analysis

The expected sensitivity for ST Monitoring Feature will be estimated by the number of true positive events divided by the total number of ACS events.

The 95% confidence limits will be calculated for sensitivity using the Wilson score interval method⁷ for a binomial proportion. The null hypothesis will be rejected if the lower bound of the 95% confidence limit is greater than 50%.

Additional Analysis

An empirical analysis will be provided for the sensitivity of the ST Monitoring Feature to detect clinical events using the estimator described in the Primary Analysis section. The standard error of this empirical estimate will be calculated as the standard deviation of a bootstrap distribution. The bootstrap distribution will be constructed using 1,000 bootstrap resamples. Each bootstrap resample will be performed at the patient level (in order to preserve the correlation structure of multiple events within one patient, if the occurs), and each resample will have a total sample size equal to the total number of evaluable patients. A two-sided 95% bootstrap confidence interval will be provided.

Subgroup Analysis

The analysis of the primary efficacy endpoint will be performed on the following subgroups of patients

- Coronary artery disease patients with cardiomyopathy
- Coronary artery disease patients without cardiomyopathy
- Patients with abnormal baseline ECGs, for each of six abnormal subgroup categories
- Patients with normal baseline ECGs
- Patients with arrhythmias
- Gender
- Patients alerted via Merlin.net and patients alerted via device Patient Notifier

Sample Size

[REDACTED]

The patients to be enrolled in the Analyze ST IDE Study are similar to those

[REDACTED]

the total number of patients required to be enrolled is 5,228.

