3.2 Clinical Event Description and CEC Adjudication

Three types of events are defined in the sections below. All clinical events will be adjudicated by a Clinical Events Committee (CEC) consisting of a blinded panel of independent experts. Once the CEC adjudicates the Clinical Events, and per defined criteria in section 3.2.2, all Type I ST episodes will be classified as either False Positive or True Positive events. In addition, any Clinical Event that was not associated with a Type I ST episode detection will be classified as either False Negative or True Negative.

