3.2.3 Classification of Events

True Positive (TP): A Type I ST episode detection that occurs up to 72 hours prior to an ACS Event.

False Positive (FP): A Type I ST episode detection that occurs more than 72 hours prior to an ACS Event or that occurs in the absence of a true ACS Event.

True Negative (TN): Absence of a Type I ST episode detection during a Non Event.

False Negative (FN): Absence of a Type I ST episode detection within 72 hours prior to an ACS Event.

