- Formation of hematomas or cysts
- Infection
- Myocardial infarction
- Peripheral nerve injury
- Pneumothorax
- Pseudo-aneurysm
- Stent thrombosis
- Stroke
- Thromboemboli
- Venous occlusion
- Venous or cardiac perforation

Analysis

- A Kaplan-Meier estimate of the proportion of patients free from complications arising from a false positive event through the 6 month follow-up visit will be provided with a 95% lower bound on the estimate using Greenwood's formula for the variance of the Kaplan-Meier estimator. If no events have been observed, then a Clopper-Pearson 95% exact lower confidence bound for the proportion of patients free from complications due to unnecessary procedures resulting from false positive events will be provided.
- A tabular presentation of ER visits, doctor office visits, or any medical care will be presented, stratified by false positive, true positive and false negative events.
- The proportion of patients with false positive events, with the count of false positive, true positive and false negative events will be provided. A preliminary estimate of sensitivity will be calculated.
- The proportion of patients with the ST monitoring feature turned off after the Programming and Baseline visits will be tabulated along with the reason for the turning off the ST monitoring feature.
- Baseline demographics and site enrollment will be tabulated.

Statistical Analysis Plan

The above analyses will be presented overall and by the following subgroups:

- Coronary artery disease patients with cardiomyopathy
- Coronary artery disease patients without cardiomyopathy
- Patients with abnormal baseline ECGs, for each of six abnormal subgroup categories
- Patients with normal baseline ECGs
- Patients with arrhythmias
- Gender
- Patients alerted via Merlin.net and patients alerted via device Patient Notifier

Additional Analysis

An analysis will be performed that includes all clinical events using a GEE logit-link linear model to estimate the sensitivity with a working correlation that provides a robust estimator of the variance adjusting for multiple clinical events within patients.

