4.7.4 Positive Predictive Value (PPV)

The PPV will be calculated as the proportion of true positives (according to section 3.2.3) to the number of all Type I ST episodes (i.e., combination of all true positive and false positive events).

$$PPV = \frac{TP}{TP + FP}$$

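### The primary sensitivity ratio counts detections in the numerator and ACS Events in the denominator, and no visible rule scores each ACS Event once

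*Protocol*

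**What the plan says.** The wording on this point is the same in the Protocol and the SAP.

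- **Formula (4.4.1).** Sensitivity is "the number of True Positive events (as defined in section 3.2.3) divided by the total number of ACS clinical events". The null hypothesis of 50% or less is rejected if the lower 95% Wilson limit exceeds 50%.
- **Unit of a True Positive (3.2.3).** "A Type I ST episode detection that occurs up to 72 hours prior to an ACS Event".
- **Unit of a False Negative (3.2.3).** "Absence of a Type I ST episode detection within 72 hours prior to an ACS Event". This is a property of an ACS Event.
- **Labelling (3.2).** On the one hand, "all Type I ST episodes will be classified as either False Positive or True Positive events". On the other, "any Clinical Event that was not associated with a Type I ST episode detection will be classified as either False Negative or True Negative". Positives are thus labels on episodes, and negatives are labels on clinical events.
- **PPV (4.7.4).** The denominator is "the number of all Type I ST episodes (i.e., combination of all true positive and false positive events", so TP is again an episode count.

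Several places point to scoring by event instead. The sentence under the formula in 4.4.1 begins "A clinical event is considered to be related to the onset of a Type I ST episode", which classifies the event and not the episode. The Wilson interval is specified for a binomial proportion. The GEE analysis in 4.3.1 "includes all clinical events using a GEE logit-link linear model to estimate the sensitivity". The bootstrap text in 4.4.1 speaks of multiple events within a patient, and the poolability model in 4.6 is a logit model for sensitivity.

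The visible counting rules cover other things. Section 3.2.2 merges precursor symptoms with the ACS Event that follows. Section 4.3.3 limits false positives to one per follow-up period and two per patient in the secondary safety endpoint.

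**The concern.** A proportion needs a numerator that is a subset of its denominator. Here the cross-reference to 3.2.3 brings a count of detections into a ratio over ACS Events. The two counts match only when every detected ACS Event has exactly one detection and no detection precedes two events.

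Repeat episodes are foreseeable: the one-per-period rule in 4.3.3 exists because several Type I episodes can occur between two device evaluations. That rule does not extend to true positives.

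This ratio decides the primary efficacy hypothesis. Repeat detections push it towards success and shared detections push it towards failure, with no change in how many ACS Events the device detected. The preliminary sensitivity estimate in 4.3.1 and the 14-day re-analysis in 4.7.15 inherit the same ambiguity, and the longer window leaves more room for repeats and for shared detections.

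**Working it through.** **Inputs.** The null value of 50%, the Wilson method and the 95% limit come from 4.4.1. The number of ACS Events is taken as n = 41. That is an assumption: 3.1 and 4.5 of the Protocol set the cut-off at a minimum of 41 clinical events, and clinical events include Non Events. The derivation of 41 is redacted, so it cannot be reproduced.

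**1. Decision boundary.** With p = k/n and z = 1.96, the Wilson lower limit is

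L = [p + z²/(2n) − z·√(p(1−p)/n + z²/(4n²))] / (1 + z²/n).

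For n = 41, z²/(2n) = 0.0468, z²/(4n²) = 0.000571 and 1 + z²/n = 1.0937.

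- k = 27: p = 0.6585, root = √(0.005485 + 0.000571) = 0.0778, L = (0.7054 − 0.1525)/1.0937 = **50.5%**, success.
- k = 26: p = 0.6341, root = √(0.005659 + 0.000571) = 0.0789, L = (0.6810 − 0.1547)/1.0937 = **48.1%**, failure.
- k = 42: p = 1.0244, and the term under the root is −0.000609 + 0.000571 = −0.000038, so no limit exists.

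**2. One repeat detection.** Suppose 26 ACS Events are detected, 15 are missed, and one detected event has a second detection.

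- By the formula: TP = 27, 27/41 = 65.9%, success.
- By event: 1 − FN/ACS = 1 − 15/41 = 63.4%, failure.
- Check: TP + FN = 27 + 15 = 42, not 41.

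**3. One shared detection.** Suppose 27 ACS Events are detected and one detection precedes two of them. Each episode carries one label, so TP = 26 and the result is a failure (48.1%). By event it is 27/41, a success (50.5%).

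**4. Effect on the error rate.** Let D be the number of detected events, D ~ Binomial(41, s), and TP = D + Poisson((m − 1)·D), where m is the assumed mean number of detections per detected event. No detections are shared. Success is 27 ≤ TP ≤ 41, so only computable intervals count. Exact results at s = 0.50:

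| m | Chance of success |
|---|---|
| 1.0 (event-level rule) | 3.0% |
| 1.05 | 7.9% |
| 1.1 | 14.9% |
| 1.2 | 32.4% |
| 1.35 | 57.6% |
| 1.5 | 72.9% |

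If each detected event has at most two detections, the figures at m = 1.05, 1.1 and 1.2 are 7.9%, 14.8% and 32.2%. The shape of the repeat distribution therefore matters little at low repeat rates.

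**5. Other numbers of ACS Events**, s = 0.50:

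| n | Count needed | m = 1.0 | m = 1.1 |
|---|---|---|---|
| 30 | 21 | 2.1% | 11.0% |
| 35 | 24 | 2.0% | 11.4% |
| 50 | 32 | 3.2% | 17.0% |
| 60 | 38 | 2.6% | 16.3% |

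The boundary is one count wide at each n, so the possibility of a flip does not depend on n = 41.

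**The case against.** The strongest reply is that the event-level rule can almost be derived from the plan. Section 3.2 separates clinical events by whether a detection was associated with them, 3.2.3 makes an undetected ACS Event a False Negative, and a binomial interval makes sense only for yes/no scores. A statistician who saw a ratio above 100% would know the count was wrong. This stands as evidence of intent, and it limits how serious the point is. It does not remove the explicit cross-reference, which a programmer could follow without ever reaching 100%: 27/41 looks entirely ordinary.

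The documents also give no repeat rate, so the larger error rates rest on assumed means. That is correct. A single repeat, moreover, changes the decision only when exactly 26 of 41 events are detected. The probability of that is 2.9%, 12.6%, 8.5% and 3.3% at true sensitivities of 50%, 65%, 70% and 75%. That is also correct, although several repeats widen the range of affected results.

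A detection before two ACS Events might be read as a True Positive for each. Section 3.2 gives each episode a single label and 4.7.4 counts each episode once, so this reading is the weaker one. How often it would arise is unknown.

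Last, a counting rule may sit in the redacted sample-size text, in the redacted sensitivity appendix or in the separate investigational protocol that 4.7.10 mentions. That cannot be excluded, so the finding is confined to the visible text. The cross-reference in 4.4.1 points to 3.2.3 and to none of those places.

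**Conclusion.** The concern holds. As written, the primary efficacy formula mixes two units, and it gives a wrong sensitivity whenever repeat and shared detections do not cancel out. Event-level scoring was very probably intended, so this is a defect in the stated rule and not in the design. It should be fixed because one count can reverse the primary conclusion in either direction.

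What is firm is the mismatch of units and the one-count boundary, 26 against 27 at n = 41. The inflation from 3.0% to 7.9%, 14.9% or 32.4% is conditional on a true sensitivity of 50%, 41 ACS Events, no shared detections, and assumed means of 1.05, 1.1 or 1.2 detections per detected event. If no detected event has a repeat and no detection is shared, the two readings agree and nothing changes.

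**What to change.** In 3.2.3 or 4.4.1 of both documents, define sensitivity as the number of ACS Events preceded within 72 hours by one or more Type I ST episode detections, divided by all ACS Events, with each ACS Event scored once. This equals 1 − FN/ACS. Add a clause that a detection falling within 72 hours before two ACS Events is credited to each of them.

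Apply the same rule to the preliminary sensitivity estimate in 4.3.1 and, with its own window, to the 14-day re-analysis in 4.7.15. Keep the episode-level True Positive for PPV only. If a counting rule already exists in text not visible here, a reference to it in 4.4.1 is enough.

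The cost is one sentence and one clause. No new data are needed, and the sample size, the Wilson decision limit and the supportive analyses stay as planned. Reported sensitivity will be lower than under the literal formula where repeat detections occur, and higher where one detection precedes two ACS Events.
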